5.4 SUBGROUPS

The following subgroups will be analysed:

- Sequence of dosage (50 mg → 100 mg vs. 100 mg → 50 mg vs. 100 mg → 200 mg vs. 200 mg → 100 mg vs. 200 mg vs. 50 mg)
- Medication history* (prior conventional systemic treatment, prior biologic, prior JAKi, none of those)
- Dosage switchers (patients who switched from abrocitinib vs. patients who remain on abrocitinib)
- Abrocitinib responder, defined as: EASI-75-responder and/or SCORAD-75-responder and/or IGA 0/1
- EASI-90 responder (yes vs. no)

If less than 20 patients are in one subgroup class, classes will be combined in a meaningful way or the subgroup analysis will be omitted with reason.

*Pfizer will assign the prior medication documented to (i) topical (TCS,TCI,other), (ii) systemic (conventional, biologics, JAKi, other), (iii) phototherapy and (iv) other in order to analyze the pretreatment and form the subgroup "medication history" accordingly.

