9.2.3. Study Period

The planned observation period of each patient is 12 months. In this time period up to 6 visits will be documented.

Figure 2. Study Period Start of Month 1 data Month 3 data Month 6 data Month 9 data Month 12 data collection collection collection collection 9 12 0 3 6 1

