9.2.4.5. Treatment of Atopic Dermatitis with Abrocitinib

At the baseline visit (Visit 1) reason of starting or re-starting treatment with abrocitinib will be documented. At each visit (Visit 1-6) dose of treatment with abrocitinib and reason for its choice will be documented. If an escalation or a de-escalation of dosage occurred since the last visit, in addition stop date of previous dosage, start date of new dosage and reason for switch (lack of efficacy or intolerability) will be documented.

If treatment with abrocitinib got terminated since the last visit, reasons for ending abrocitinib treatment, stop date of treatment, start date of other new treatment and reason for switch (lack of efficacy or intolerability) will be documented.

At Visits 2-6, the investigator will ask the patient for his or her self-assessment of compliance in terms of number of abrocitinib-free days since the last visit.

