
1.2 STUDY POPULATION

In total, this non-interventional study aims to enroll at least 750 patients patients at approximately 80 study sites across Germany. The planned enrollment period is 48 months. With a planned observation duration of 12 months per patient, the entire study would last for 60 months. The non-interventional study started in April 2022 and will end in May 2027.

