4 HYPOTHESES AND DECISION RULES

As the protocol states, this is a solely descriptive and explorative non-interventional study with the aim to generate hypothes. In order to generate hypotheses the statistical tests mentioned in section 8.2.3 are carried out for the subgroups defined in section 5.4.

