8.2.3 Summary of Analyses

Outcome	Analysis Set	Supports Protocol Objective Number	Subgroups	Statistical Method	Covariates/ Strata	Missing Data
Response based on achieving the IGA of clear (0) or almost clear (1) (on a 5-point scale) at month 3	FAS, mFAS, PP	1	All	Percentage of patients with IGA score 0 or 1 at month 3 Chi-Square test respective Fisher's exact test for subgroups	None	Excluded
Response based on achieving the EASI-75 at month 3	FAS, mFAS, PP	2	All	Percentage of patients with 75% reduction from baseline in EASI at month 3 Chi-Square test respective Fisher's exact test for subgroups	None	Excluded
Response based on achieving the IGA of clear (0) or almost clear (1) (on a 5-point scale)	FAS, mFAS, PP	3	All	Percentage of patients with IGA score 0 or 1 irrespective of the point in time Chi-Square test respective Fisher's exact test for subgroups	None	Excluded
Response based on achieving the EASI-75	FAS, mFAS, PP	4	All	Percentage of patients with 75% reduction from baseline in EASI irrespective of the point in time Chi-Square test respective Fisher's exact test for subgroups	None	Excluded

Outcome **Analysis Set Supports Missing Data** Subgroups Statistical Method Covariates/ Strata Protocol **Objective** Number Response based on FAS, mFAS, PP All Percentage of patients None Excluded achieving the EASI-90 with 90% reduction from baseline in EASI irrespective of the 5 point in time Chi-Square test respective Fisher's exact test for subgroups Percentage of patients Response based on FAS, mFAS, PP Excluded All None achieving the IGA of with IGA score 0 or 1 clear (0) or almost clear and a reduction from (1) and a reduction from baseline of ≥ 2 points baseline of ≥2 points irrespective of the 6 point in time Chi-Square test respective Fisher's exact test for subgroups Percentage change of FAS, mFAS, PP (score at respective All None Excluded IGA compared to visit - score at baseline baseline)/score at 7 baseline*100 Mann-Whitney-U test for subgroups (score at respective Percentage change of FAS, mFAS, PP All None Excluded SCORAD compared to visit - score at baseline baseline)/score at baseline*100 Mann-Whitney-U test for subgroups Absolute EASI values FAS, mFAS, PP All Summary statistics (n, None Excluded mean, median, over time standard deviation, 9 minimum and maximum) of the score at each point in time

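### Month-3 response is tested across dose-sequence and switch/remain classes that later, response-driven dose changes can define, so the test can show differences when dose has no effect

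*SAP*

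**What the plan says.** - **Subgroups.** SAP 5.4 lists dose-sequence classes, beginning "Sequence of dosage (50 mg → 100 mg vs. 100 mg → 50 mg vs. 100 mg → 200 mg", and a separate grouping of patients who switched from abrocitinib against those who remain on it. Neither has a time limit. In the text as read, 50 mg and 200 mg also appear as constant-dose classes.
- **When dose is recorded.** Protocol 9.2.4.5: "At each visit (Visit 1-6) dose of treatment with abrocitinib and reason for its choice will be documented". Protocol 9.2.3: "The planned observation period of each patient is 12 months". Under SAP 3 the final analysis follows the month-12 visit.
- **Why dose changes.** Protocol 9.2.4.5 asks for dates at each escalation or de-escalation, including "start date of new dosage and reason for switch (lack of efficacy or intolerability) will be documented". It asks for the same reasons when abrocitinib is ended.
- **What is tested.** SAP 4: "In order to generate hypotheses the statistical tests mentioned in section 8.2.3 are carried out for the subgroups defined in section 5.4". For the first primary endpoint, SAP 8.2.3 marks all subgroups and gives "Percentage of patients with IGA score 0 or 1 at month 3 Chi-Square test respective Fisher's exact test for subgroups". EASI-75 at month 3 is treated the same way.
- **Adjustment.** SAP 6.4 gives no covariates, and the covariate column of 8.2.3 reads none throughout. There is no landmark or time-varying dose method, and no subgroup by starting dose.

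**The concern.** A subgroup comparison of a month-3 outcome is interpretable if the subgroup is fixed before that outcome. Here it need not be. A patient who has not responded at month 3 and is then escalated enters an escalation class because of that result, while a comparable responder stays in a constant-dose class. A dose first taken after month 3 cannot have influenced month-3 IGA or EASI, yet it decides which column the patient is counted in.

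Escalation for lack of efficacy pushes the escalated classes towards low month-3 response even if every dose works equally well. The switch/remain grouping has the same structure, since lack of efficacy is also a recorded reason for ending abrocitinib. At stake are the dose-related hypotheses drawn from the primary endpoints.

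**Working it through.** The plan gives no figure to reproduce: there is no power calculation, significance level, assumed response rate or dose-change rate. What can be checked is how the planned test behaves when dose truly has no effect.

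**Inputs from the documents.** The listed SAP 5.4 classes; the minimum class size of 20 (SAP 5.4); the chi-square test (SAP 8.2.3); and the target N, as the SAP "aims to enroll at least 750 patients".

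**Assumptions.** Month-3 response 50% at every dose; starting doses 50/100/200 mg in 10/45/45% of patients; two-sided 5% level; de-escalation unrelated to response. Each scenario was simulated 1,500 times.

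**Closed form, one change after month 3.** Let p be month-3 response, and a and b the escalation probabilities in non-responders and responders.

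- Response in the escalated class = p·b / (p·b + (1−p)·a).
- a = 20%, b = 10%: 0.05 / (0.05 + 0.10) = 33%.
- a = 30%, b = 10%: 0.05 / (0.05 + 0.15) = 25%.
- Patients starting on 200 mg have no escalation class, so the constant 200 mg class stays at 50%. The gaps are 17 and 25 points.
- Against a constant class with the same starting dose the gap is wider, because that class keeps the responders. For constant 50 mg: 0.45 / (0.45 + 0.40) = 53% in the first case and 0.45 / (0.45 + 0.35) = 56% in the second, giving gaps of 20 and 31 points.

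**Simulated rejection rates, zero dose effect, N = 750.** In the visit-by-visit model the first change may occur at month 1, 3, 6 or 9 and depends on response at that visit; the latent correlation between visits is 0.3 to 0.7.

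| Dose-change rule (non-responders v responders) | 100→200 v constant 200 | Rejection |
|---|---|---|
| Change unrelated to response | 50% v 50% | 5-6% |
| Visit by visit, 10% v 5% (weak) | 41-44% v 50% | 11-24% |
| Visit by visit, 10% v 2% | 31-38% v 50% | 33-75% |
| Visit by visit, 15% v 2% | 28-37% v 50% | 57-96% |
| One step, 20% v 10% | 33% v 50% | 45% |
| One step, 30% v 10% | 25% v 50% | 93% |

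The first row shows that the test itself is sound; the excess comes from how the classes are formed. Grouping the same simulated patients by starting dose gave 3.5-6.2% rejection in all scenarios. That result assumes starting dose is unrelated to prognosis.

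**The case against.** The strongest reply is that the plan claims little for these tests. SAP 8.2 calls the subgroup tests exploratory, SAP 4.2 sets no decision rules, and Protocol 9.9 warns about causality and confounding. Reasons for the prescribed dose are also to be tabulated by subgroup, so a careful reader could see why patients were in each class. This stands as a limit on the consequence. It does not remove the bias: an exploratory label covers multiplicity and strength of claim, not a grouping shaped by the outcome it is compared on, and SAP 4 says the tests exist to generate hypotheses.

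The second reply is that the size is unknown. That is right. Under weak dependence the artefact is modest, and changes made purely for intolerability need not track response at all.

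A reader might also infer more than the documents support:

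- **That the SAP defines a 12-month sequence.** It does not say so. The span is inferred from the missing cut-off and from dose recording at Visits 1 to 6.
- **That the differences must be large.** This depends on change rates that are not given.
- **That de-escalated classes will look better.** This needs dose reduction after good response, which Protocol 9.2.4.5 does not list as a reason.
- **That the study's stated purpose is to guide dosing.** The remark about optimising future therapy closes a rationale section (Protocol 7.4); no objective is a dose comparison.

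**Conclusion.** The concern holds in this form: as written, the plan compares month-3 response across classes that can be partly formed by that response, and nothing in the SAP corrects for it. With no dose effect, escalation for non-response makes escalated classes look worse. The gap to constant 200 mg runs from 6-9 points (11-24% rejection) under weak dependence to about 25 points (93% rejection) in the stronger one-step case shown. These sizes rest on assumed response, dose-change and starting-dose rates and an assumed 5% level. No size was calculated for the switch/remain grouping; the argument there is structural. The overall month-3 IGA and EASI-75 percentages do not use these classes and are unaffected. The point should be corrected but does not threaten the main result.

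**What to change.** In SAP 5.4 and 8.2.3:

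1. Use the dose documented at Visit 1 as the tested dose subgroup for both month-3 primary endpoints and for the by-visit response endpoints.
2. Neither test nor tabulate month-3 response by dose-sequence or switch/remain classes that include changes after the month-3 visit. Dropping only the test would leave the same misleading percentages in the tables. Keep these classes for describing treatment patterns.
3. State that the physician chooses the starting dose and that, in patients re-starting abrocitinib (eligible under Protocol 9.2.1), it may reflect earlier response. The contrast therefore remains confounded by indication.
4. If EASI or IGA before and after a dose change is shown, label it descriptive and subject to regression to the mean, because patients escalated for poor response are selected at a bad point.

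The cost is SAP wording and revised table shells. No new data are needed, since dose is already recorded at Visit 1. The downside is that starting-dose groups say nothing about later dose changes, which the descriptive sequence tables would still cover.

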Abrocitinib selectively inhibits JAK-1 by blocking the adenosine triphosphate (ATP) binding site. It has a high degree of selectivity against other kinases in the human genome: 28-fold selectivity over JAK-2, >340-fold over JAK-3 and 43-fold over tyrosine kinase 2 (TYK2) as well as a good selectivity profile over the broader range of human kinases. A variety of pro-inflammatory cytokines such as IL-4, IL-5, IL-13, IL-31 and IFN-γ, have been suggested to be involved in the pathogenesis of AD. Many of these pathogenic cytokines use JAK-1 for signaling. This suggests that selective JAK-1 inhibitors that modulate the activity of these cytokines represent a compelling approach to the treatment of inflammatory skin diseases such as AD [17]. Broader inhibition of cytokines, including those important in the pathogenesis of AD, may result in an increased proportion of responders, with an acceptable safety profile.

The first Phase 3 studies, B7451012 and B7451013, that evaluated 100 and 200 mg once daily (QD) abrocitinib in participants with moderate to severe AD, which were completed in 2019, reported statistically significant improvement in efficacy endpoints in both treatment groups compared to the placebo group, with an acceptable safety profile [18,19].

Summary of Study Rationale

Currently, there is a lack of real-world data regarding the effectiveness of the new systemic treatment class of JAK inhibitors in AD in daily clinical practice in Germany. Thus, this non-interventional study was designed to gather information about non-selected patients who have been chosen to start treatment with abrocitinib in dermatological practices in Germany.

In order to gain valuable and solid insights into current and upcoming real-world treatment patterns starting with a systemic abrocitinib therapy, all subsequent therapy sequences with reasons for the respective therapy decisions will be systematically documented. Specific information on the patient's medical and clinical history, the routine clinical management including the reasons for starting treatment, management of treatment initiation, prescribed concomitant medication, its dosage, and actual use by the

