Outcome **Analysis Set Supports Missing Data** Subgroups Statistical Method Covariates/ Strata Protocol **Objective** Number baseline)/score at baseline*100 Mann-Whitney-U test for subgroups Change of EuroQol five-(score at respective FAS, mFAS, PP All None Excluded dimensional-five level visit - score at (EQ-5D-5L) from baseline)/score at 21 baseline baseline*100 Mann-Whitney-U test for subgroups Change of PBI from FAS, mFAS, PP All (score at respective None Excluded visit - score at baseline baseline)/score at 22 baseline*100 Mann-Whitney-U test for subgroups Patient's satisfaction FAS, mFAS, PP All Frequency tables for None Excluded satisfaction with with treatment (PBI after baseline) effectiveness and tolerability 23 Chi-Square test respective Fisher's exact test for subgroups Number of days with FAS, mFAS, PP All Excluded Summary statistics (n, None topical-treatment use mean, median, standard deviation, (TCS, TCI) 24 minimum and maximum) Mann-Whitney-U test for subgroups Number of days with FAS, mFAS, PP All Summary statistics (n, None Excluded emollients use mean, median, standard deviation, 25 minimum and maximum)

Outcome	Analysis Set	Supports Protocol Objective Number	Subgroups	Statistical Method	Covariates/ Strata	Missing Data
				Mann-Whitney-U test for subgroups		
AD-treatment with abrocitinib and/or without topicals – total days	FAS, mFAS, PP	26	All	Summary statistics (n, mean, median, standard deviation, minimum and maximum) Mann-Whitney-U test for subgroups	None	Excluded
AD-treatment with abrocitinib and/or without topicals – stratified by abrocitinib dose	FAS, mFAS, PP	27	All	Summary statistics (n, mean, median, standard deviation, minimum and maximum) Mann-Whitney-U test for subgroups	None	Excluded
Number of flares	FAS, mFAS, PP	28	All	Summary statistics (n, mean, median, standard deviation, minimum and maximum) Mann-Whitney-U test for subgroups	None	Excluded

All explorative endpoints mentioned in section 6.3 will be analyzed for FAS and all subgroups, respectively. Safety enpoints, as given in section 6.2 will be analyzed for SAF.

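### SAP 5.4 gives no dose-sequence class to patients who stay on 100 mg, and no residual class, so they fall out of the exploratory dose-sequence comparisons

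*SAP*

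**What the plan says.** The subgroup list in SAP 5.4 opens with "Sequence of dosage (50 mg → 100 mg vs. 100 mg → 50 mg vs. 100 mg → 200 mg" and closes with "200 mg → 100 mg vs. 200 mg vs. 50 mg". That makes six classes: four with one dose change and two with a single dose.

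The section has one rule for sparse data: "If less than 20 patients are in one subgroup class, classes will be combined in a meaningful way or the subgroup analysis will be omitted". A second subgroup also carries dosage in its name: "Dosage switchers (patients who switched from abrocitinib vs. patients who remain on abrocitinib".

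SAP 4 explains the purpose of the subgroups: "In order to generate hypotheses the statistical tests mentioned in section 8.2.3 are carried out for the subgroups defined in section 5.4". In the SAP 8.2.3 table every outcome row, including IGA 0/1 and EASI-75 at Month 3, has the entry All in the subgroup column. The note under the table adds: "All explorative endpoints mentioned in section 6.3 will be analyzed for FAS and all subgroups, respectively".

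On the doses themselves, SAP 1 says that the first Phase 3 studies "evaluated 100 and 200 mg once daily (QD) abrocitinib in participants with moderate to severe AD".

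**The concern.** A subgroup variable should give every patient a place. This one gives a place to unchanged 200 mg and unchanged 50 mg but not to unchanged 100 mg, although 100 mg is the start or end of all four change classes. The authors plainly expected 100 mg to be used, and no reason for the omission is given. It looks like an oversight.

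Three things follow if the SAP is programmed as it stands:

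- Patients who stay on 100 mg, and those with an unlisted path, are missing from each dose-sequence table, and the class totals need not add up to the FAS.
- Inside this subgroup, 100 mg is represented only by patients whose dose was changed. Protocol 9.2.4.5 records the reason for such a switch as lack of efficacy or intolerability, so they are selected on how treatment went.
- Unchanged 200 mg stands beside changed-dose patients and unchanged 50 mg only. A reader could take that table for a description of outcome by dose, which it would not be.

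Protocol 9.5 says that the sample size was chosen so that results would be usefully precise in subgroups too. An incomplete class list works against that aim.

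**Working it through.** The plan has no figure to reproduce: Protocol 9.5 states that a formal sample size calculation does not apply. The check is an enumeration, a search for text that might fill the gap, and an illustration of size.

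**Step 1. Enumerate the paths.** SAP 5.4 names three doses: 50, 100 and 200 mg. With at most one change there are 3 unchanged paths and 3 × 2 = 6 ordered changes, so 3 + 6 = 9.

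| Path | In SAP 5.4? |
|---|---|
| 50 unchanged | yes |
| 100 unchanged | **no** |
| 200 unchanged | yes |
| 50→100 | yes |
| 100→50 | yes |
| 100→200 | yes |
| 200→100 | yes |
| 50→200 | **no** |
| 200→50 | **no** |

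Six of nine are listed and three are missing. Unchanged 100 mg is the only unchanged dose without a class. Paths with two or more changes, such as 200→100→200, have no class either.

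**Step 2. Look for text that fills the gap.**

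- The fewer-than-20 rule in SAP 5.4 merges or drops listed classes. It does not create a class or place a patient who has none.
- The switcher subgroup in SAP 5.4 separates leaving abrocitinib from staying on it. It does not separate doses.
- SAP 6.3 and 8.2.3 summarise treatment duration by each patient's most frequently used dose. Users of 100 mg are included, but the outcome is duration rather than response, and unchanged and changed patients are mixed.
- The dosage variable in SAP 6.3 is summarised as a quantity and forms no groups.
- SAP 6.4 and the covariate column in 8.2.3 specify no covariates, so no model recovers a dose contrast.

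None of these supplies the missing class.

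**Step 3. Size.** The documents give no dose distribution. Assume that share *s* of the planned 750 stays on 100 mg and that the FAS is close to 750. Patients without a class = *s* × 750, before counting the other unlisted paths:

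| Assumed share | Patients without a class |
|---|---|
| 10% | 75 |
| 20% | 150 |
| 30% | 225 |
| 40% | 300 |

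The SAP's own minimum class size is 20, and 20 / 750 = 2.7%. Any share above that would make unchanged 100 mg large enough to stand as a class.

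**Step 4. What the added class would allow.** For a difference in response between unchanged 100 mg and unchanged 200 mg, the worst-case 95% half-width (response 50% in each) is 1.96 × √(0.25/n₁ + 0.25/n₂). With equal assumed shares:

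- 10% each (75 and 75): 1.96 × √(0.25/75 + 0.25/75) = 0.160, about ±16 percentage points
- 20% each (150 and 150): 0.113, about ±11 points
- 30% each (225 and 225): 0.092, about ±9 points
- 40% each (300 and 300): 0.080, about ±8 points

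**The case against.** The strongest reply is that little depends on this subgroup. SAP 4.1 and 4.2 state no hypotheses or decision rules, and SAP 8.2 calls the subgroup tests purely explorative. Both primary endpoints are overall percentages, and patients who stay on 100 mg count fully in them. They also remain in the other subgroups and in the safety set. All of this stands, and it limits the severity.

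Four stronger readings are tempting, and the documents do not support them:

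- *That 100 mg drops out of every comparison by dose.* It does not: the treatment-duration summary by most-used dose keeps these patients. The gap is confined to the dose-sequence subgroup.
- *That one of the study's main exposure groups is lost.* Being one of two Phase 3 doses named in the background does not show how many patients stay on 100 mg in routine care. The counts above are assumed shares.
- *That a study objective is defeated.* The explorative objective is to document dosage and actual use, and the dosage and dose-reason summaries in SAP 6.3 do that for the whole FAS. No objective asks for effectiveness to be compared between doses.
- *That a planned contrast of unchanged 200 mg with unchanged 100 mg has been broken.* None is planned. SAP 8.1 names the tests but no pairwise scheme across six classes. Any such contrast would also be non-randomised, with dose chosen by the physician.

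It can also be said that no text requires the classes to be exhaustive, and that the table shells cited in SAP 9 may already contain the class. Both are fair. The shells are a separate document that was not available here; if they do contain it, the SAP text should match. If they do not, the SAP as written gives no instruction for these patients.

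**Conclusion.** The gap is real and narrow. SAP 5.4 has no class for patients who stay on 100 mg, and none for 50→200, 200→50 or several changes. As written, these patients are left out of every exploratory dose-sequence comparison under SAP 4 and 8.2.3, including those for IGA 0/1 and EASI-75 at Month 3.

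The overall primary, secondary and safety estimates do not change, nor does the treatment-duration summary by most-used dose. How many patients are affected cannot be known from the documents; 75 to 300 corresponds to an assumed 10% to 40% of 750.

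The conclusion rests on reading the bare 200 mg and 50 mg entries as unchanged dosing, the natural sense in a list of sequences. On any reading, 100 mg alone has no entry.

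Severity: should-fix, exploratory subgroup only. The point concerns analysis classes and says nothing about which dose is appropriate.

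**What to change.** Before database lock, add two classes to the dose-sequence subgroup in SAP 5.4:

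- 100 mg (unchanged);
- other / more than one dose change, which takes every path not otherwise named, including 50→200 and 200→50.

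State that every FAS patient falls in exactly one class, so that the class totals equal the FAS. Apply the existing fewer-than-20 rule to any small class, and bring the table shells into line.

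The cost is a line or two of SAP text and two more columns in the dose-sequence tables, some of which may be merged under the existing rule. No new data are needed: under Protocol 9.2.4.5 the dose is documented at each visit, and the stop and start dates when it changes. Made before lock, the change is part of the plan; made after results are seen, it would be a post hoc choice.

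Rebuilding the classes visit by visit from the dose history to date is a separate question. It would let a patient change class between visits, contrary to the one-class rule, and is not part of this fix.

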6.1 EFFICACY/EFFECTIVENESS ENDPOINT(S)

Effectiveness endpoints comprise of all primary and secondary endpoints, i.e. effectiveness, and quality parameters assessed by the physicians and the patients.

Primary endpoint analysis

Variable	Role	Data source(s)	Operational definition
EASI	Primary outcome variable	Case records	Percentage of patients with 75% reduction from baseline in EASI at month 3
IGA	Primary outcome variable	Case records	Percentage of patients with IGA score 0 or 1 at month 3

Secondary endpoint analysis

Variable	Role	Data source(s)	Operational definition
SCORAD	Secondary outcome variable	Case records	Summary statistics (n, mean, median, standard deviation, minimum and maximum) of the total score and SCORAD-A at each point in time, respectively as well as the respective percentage change to baseline
EASI	Secondary outcome variable	Case records	 Percentage of patients with 75% reduction from baseline in EASI irrespective of the point in time Percentage of patients with 90% reduction from baseline in EASI irrespective of the point in time Summary statistics (n, mean, median, standard deviation, minimum and maximum) of the score at each point in time as well as the respective percentage change to baseline
IGA	Secondary outcome variable	Case records	 Percentage of patients with IGA score 0 or 1 irrespective of the point in time Percentage of patients with IGA score 0 or 1 and a reduction from baseline of ≥2 points irrespective of the point in time Summary statistics (n, mean, median, standard deviation, minimum and maximum) of the score at each point in time as well as the respective percentage change to baseline ((score at respective visit – score at baseline)/score at baseline*100)

Pruritus- NRS	Secondary outcome variable	Case records	Percentage of patients achieving at least 4 points improvement of Pruritus NRS from baseline Summary statistics (n, mean, median, standard deviation, minimum and maximum) of the score at each point in time as well as the percentage change to baseline Percentage of patients with Pruritus NRS ≤1
PP- NRS	Secondary outcome variable	Case records	 Percentage of patients achieving at least 4 points improvement of PP NRS from baseline Summary statistics (n, mean, median, standard deviation, minimum and maximum) of the score at each point in time as well as the percentage change to baseline Percentage of patients with PP NRS ≤1

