11 APPENDICES

11.1 APPENDIX 1: DATA DERIVATION DETAILS

EASI-75-responder: Percentage of patients with 75% reduction from baseline in EASI EASI-90-responder: Percentage of patients with 90% reduction from baseline in EASI SCORAD-75-responder: Percentage of patients with 75% reduction from baseline Abrocitinib responder: EASI-75-responder and/or SCORAD-75-responder and/or IGA 0/1

Number of days with topical treatment use (TCS, TCI): Date of first topical treatment – date of last topical treatment + 1

Number of days with emollients use: Date of first emollients use – date of last emollients use + 1

 $\underline{Days\ of\ AD\text{-treatment:}}\ Date\ of\ last\ AD\ treatment-date\ first_AD\text{-treatment}+1$

Age [years]: Year of informed consent – year of birth

Age at initial diagnosis of AD [years]: year of initial diagnosis – year of birth

Percentage change to baseline: (score at respective visit – score at baseline)/score at baseline*100

Information of additional documentation timepoints will be added to the information of the next scheduled visit and analyzed at the scheduled visit.

PROs and other questionnaires referring to additional documentation timepoints will not be analyzed but may be of interest if the course of individual patients is considered in more detail.

PROs will be assigned to the month/scheduled visit according to the time windows given below.

A1.1 Definition and use of visit windows in interim analysis

Visit Label	Endpoint	Definition [Day window]
Enrolment	All	1
Month 1	All	2 to 44
Month 3	All	45 to 105
Month 6	All	106 to 210
Month 9	All	211 to 301
Month 12	All	302 to 393

PFIZER CONFIDENTIAL

CT24-WI-GL03-RF02 2.0 Non-Interventional Statistical Analysis Plan For Primary Data Collection Study 01-Jun-2020
Page 38 of 39

A1.2 Further definition of endpoints

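### The SAP tests EASI, IGA and SCORAD outcomes in responder subgroups defined by those same scores, gives no time point for responder status, and leaves the numerical test for six dose-sequence classes unspecified

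*SAP*

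**What the plan says.** SAP section 4 says that, to generate hypotheses, "the statistical tests mentioned in section 8.2.3 are carried out for the subgroups defined in section 5.4". In Table 8.2.3 the subgroup column reads All for every outcome, for example "Absolute EASI values FAS, mFAS, PP All". No outcome is exempted for any subgroup.

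Two of the five subgroups in SAP section 5.4 are built from study outcomes:

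- The composite: "Abrocitinib responder, defined as: EASI-75-responder and/or SCORAD-75-responder and/or IGA 0/1". No comparator is printed; non-responders are the natural one.
- "EASI-90 responder (yes vs. no"), which Appendix 1 derives as "Percentage of patients with 90% reduction from baseline in EASI".

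Neither section 5.4 nor Appendix 1 says at which visit, or over which visits, responder status is determined. The outcome rows do make that distinction: some are fixed at month 3, others are worded as "Percentage of patients with IGA score 0 or 1 irrespective of the point in time".

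For numerical data, SAP section 8.1 and each numerical row of Table 8.2.3 name the Mann-Whitney U test and nothing else. Section 5.4 prints six dose-sequence classes: four with a change between two doses, then 200 mg alone and 50 mg alone. Classes with fewer than 20 patients are to be merged or the analysis omitted.

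**The concern.** A test of an outcome between groups formed from that same outcome does not ask a question about patients. Part of the difference, and in some cells all of it, comes from the grouping. SAP section 4 gives hypothesis generation as the purpose of these tests, and a difference created by the grouping generates no hypothesis. In a large table, such rows would appear as the most striking results.

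The missing time point matters in its own right. Two programmers could take responder status at month 3, at any visit or at the last visit, form different groups from the same data, and produce different tables.

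Mann-Whitney U compares two samples. With six classes the analyst must decide whether to run an overall test, all pairs, or each class against a reference. The SAP leaves that choice open. Patients who take 100 mg throughout have no printed class at all.

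**Working it through.** The documents give no number of subgroup tests and no significance level, so there is no stated figure to reproduce. The inputs are the rows of Table 8.2.3, the definitions in section 5.4 and Appendix 1, the 20-patient rule in section 5.4, and the rule in section 8.1 that Fisher's test applies when a subgroup has fewer than 30.

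**Row count.** Table 8.2.3 has 27 outcome rows. Seventeen use Mann-Whitney U. Ten use chi-square or Fisher: nine binary and one categorical (PBI satisfaction). By the table's own numbering:

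| Score | Rows | Count |
|---|---|---|
| IGA | 1, 3, 6, 7, 11 | 5 |
| EASI | 2, 4, 5, 9, 10 | 5 |
| SCORAD | 8 | 1 |

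The composite uses all three scores: 5 + 5 + 1 = 11 pairs. EASI-90 responder uses EASI only: 5 pairs. Total 11 + 5 = 16. IGA and SCORAD rows by EASI-90 responder are correlated but not definitional, so they are not counted. If all three analysis sets are run, 16 × 3 = 48, before repeats by visit.

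**Same time rule, EASI-90 by EASI-90 responder.** Every responder meets the outcome and no non-responder does. With complete data and 20 per class, Fisher two-sided p = 2/C(40,20) = 2/137,846,528,820 = 1.5e-11. Percentage EASI change at the same visit separates completely at the 90% cut, so the exact Mann-Whitney p is the same (6.8e-8 by normal approximation).

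**Same time rule, composite.** A non-responder has by definition missed EASI-75 and IGA 0/1, and therefore EASI-90 too, so the non-responder rate in those rows is 0%. The p-value still depends on how many responders met that row's criterion. The documents give no rates, so a range is assumed. At 20 versus 20:

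| Responders meeting the criterion | Fisher p against 0/20 |
|---|---|
| 4/20 | 0.106 |
| 5/20 | 0.047 |
| 6/20 | 0.020 |
| 10/20 | 4.4e-4 |
| 18/20 | 3.4e-9 |

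With 300 assessed and 80% responders (both assumed), 72/240 versus 0/60 gives chi-square 23.7 (p = 1.1e-6), and 120/240 versus 0/60 gives 50.0 (p = 1.5e-12).

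**Different time points.** Suppose EASI-90 status is set at another visit. Assume a bivariate normal latent response with between-visit correlation 0.3 to 0.7, EASI-75 at month 3 of 40% or 60%, and EASI-90 of 30% or 50%.

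| Correlation | EASI-75 at month 3, EASI-90 yes vs no | Gap (points) | Fisher p, 20 vs 20 |
|---|---|---|---|
| 0.3 | from 49 vs 31% to 73 vs 54% | 19 to 20 | 0.32 to 0.34 |
| 0.7 | from 64 vs 16% to 91 vs 47% | 44 to 51 | 0.003 to 0.006 |

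Across the range the gap is about 19 to 51 percentage points: substantial, but not an identity.

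**Six classes.** Pairs: C(6,2) = 15 per numerical outcome. Merging does not guarantee two classes, because six classes of 20 need only 6 × 20 = 120 of at least 750 planned patients. In a simulation with no true difference, at an assumed 0.05 level, unadjusted pairwise Mann-Whitney testing gave at least one false positive in 36% of runs (20 per class) to 38% (125 per class), against 4 to 5% for one Kruskal-Wallis test.

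**The case against.** The strongest reply is that the SAP states no hypotheses or decision rules, calls the subgroup tests purely explorative, and disclaims multiplicity adjustment. That stands as a limit on the consequence. It does not make a comparison fixed by its own grouping informative, and exploration is the purpose these tests are meant to serve.

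A reader might infer that all 16 pairs are exact tautologies whose p-values are set by class size alone. The documents do not support that. It is true of EASI-90 by EASI-90 responder and of same-visit percentage EASI change, and only if status and outcome share a time rule. The composite rows also depend on which criterion responders met. The absolute EASI row includes baseline values, since SAP section 6.1 asks for summaries "of the score at each point in time as well as the respective percentage change to baseline", and baseline EASI by responder status is a legitimate comparison.

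A reader might also infer that the SAP names no usable test for dose sequence. That is too strong: the classes are set against each other one by one, and unadjusted pairwise Mann-Whitney tests are a consistent reading. What is missing is a statement of which scheme applies. Nor should medication history be counted as a second certain case. Its four categories can overlap within a patient and may be meant as separate yes/no factors, for which Mann-Whitney U fits. Chi-square and Fisher handle more than two classes, so the binary and categorical rows are unaffected.

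Finally, adding a class for 100 mg throughout does not make the dose list exhaustive, as other sequences are also unprinted. That is fair, but it does not excuse leaving out one of the three single-dose classes.

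**Conclusion.** The point holds. As written, the SAP tests 16 outcome-by-subgroup pairs in which the grouping shares a defining score with the outcome: 11 for the composite, read as responder versus non-responder, and 5 for EASI-90. How strict the circularity is depends on the unstated time point, from an exact 100% versus 0% split to a partial gap of about 19 to 51 points under the assumed correlations and response rates. The numerical test for six dose-sequence classes is under-specified, and patients on 100 mg throughout have no class.

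It would be wrong to infer that the primary results are compromised. The overall month-3 IGA and EASI-75 estimates do not use these subgroups, and only the explorative subgroup tables are affected. The conclusion rests on the SAP text; the table shells that SAP section 9 places in a separate document were not available and might already settle some of this.

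**What to change.** 1. In Table 8.2.3, do not test post-baseline EASI, IGA and SCORAD outcomes by Abrocitinib responder, nor post-baseline EASI outcomes by EASI-90 responder. Keep the comparisons of baseline scores, baseline characteristics and patient-reported outcomes, which serve the stated interest in predictors of response.
2. State one time point for responder status in section 5.4 and Appendix 1, and name non-responders as the comparator for the composite.
3. In section 8.1, use Kruskal-Wallis for numerical outcomes in any subgroup with more than two classes, and Mann-Whitney U for two.
4. Add a dose-sequence class for patients on 100 mg throughout. This is an analysis grouping, not a dosing rule.

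The cost is SAP wording and some subgroup tables removed or re-specified, with the table shells brought into line. No new data are needed.
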